After 2 weeks of home stimulation, those that are on bladder medicine will discontinue the medication. There is no other harm from rapid discontinuation of bladder medication, except for possible incontinence. The outcome measures are measure of bladder medication doses and surveys. The Incontinence Quality of Life (I-QOL) survey reflects the quality of life related to incontinence.²⁰ The Neurogenic Bladder Symptom Score (NBSS) measures and scores symptoms related to NGB.²¹ Both will be conducted at baseline and at 3-months post-discharge. The medication + TTNS adherence survey and Medication + TTNS % survey. Adherence scales will measure adherence to medication and transcutaneous tibial nerve stimulation. Will be conducted at baseline, then every 4 weeks. The Connor-Davidson Resilience Scale (CD-RISC-25) will measure resilience. Conducted at baseline, week 6 and at the end of trial. The PROMIS General Self-Efficacy (GSE) will measure self-efficacy. (There is no validated Spanish version. Therefore, a conclusion cannot be made.) Conducted at baseline, week 6 and at the end of trial.

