- Potential for progressive SCI including neurodegenerative SCI, ALS, cancer myelopathy, Multiple sclerosis, transverse myelitis
- History of central nervous system disorder (i.e. prior SCI, stroke, brain injury, Parkinson's disease, MS, etc.)
- History of peripheral neuropathy
- pre-SCI symptoms of peripheral neuropathy (numbness and/or tingling in feet, sharp/jabbing/burning pain in feet, sensitivity to touch, lack of coordination, muscle weakness, etc.)
- Pregnancy
- Known injury to the lumbosacral spinal cord or plexus, or pelvis with associated neuropathy
- concern for tibial nerve pathway injury
- absence of toe flexion or autonomic dysreflexia during electric stimulation test
- bladder chemodenervation in prior 6 months

5. Withdrawal Criteria

Possible reasons for discontinuation of study intervention:

- Intolerable incontinence after discontinuation of bladder medications
- Intolerant to electric stimulation
- Non-compliance

To mitigate non-compliance, a stipend for effort in completing voiding diary will be provided at \$10 per day (2 days per month). An additional \$20 will be provided for logging bladder medication use and TTNS use/settings monthly. If both voiding diary and TTNS diary are reported, a \$10 bonus will be provided, therefore \$70 month 1, and \$50 for each months 2 and 3. At most per subject= \$170 for the 3-month trial per subject. Subjects will also receive reimbursement for travel for the urodynamic studies up to \$200 per trip (two urodynamic studies = up to \$400 per subject) and if medication reduction requires new prescriptions to cover co-payments when applicable up to \$50 total per subject.

6. Subject Replacement

Subjects who drop out will be replaced by recruitment from the SCI clinic and asking for informed consent from those who meet the I/E criteria.

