Medication reduction protocol: Subjects will be using up to 2 anticholinergic OAB medications. Subjects generally use similar medications with a common approach- maximize one medication before adding a second medication. The PI will provide a weekly weaning schedule, individualized for each subject. No changes will occur during the first 2 weeks of TTNS. Starting week 3, the secondary OAB medication will be halved if possible, otherwise discontinued. Should the subject tolerate this, weaning will continue until one medication is discontinued, then the other. If the subject does not tolerate weaning, they will remain on the lowest, tolerable dose and we will attempt weaning the following week.

- Information gathered:
 - Clinical demographics, morbidity, and Neurologic Exam findings from interview with subjects, exam, and EMR review.
 - Bladder diary will include:
 - use of TTNS with amperage and presence of toe flexion, and pain score 0-10
 - log of catheterization, volumes
 - log of incontinence episodes
 - Description of other observed changes, including but not limited to: fatigue, vision changes, mental status, bowel program changes, and sexual function changes.
 - I-QOL at baseline initial visit and then at 3-month follow-up. Can be conducted over phone.

- NBSS at baseline and every 4 weeks (monthly) and at the 3-month follow-up. Can be conducted over phone.
- Anticholinergic survey at baseline and then at 3-month follow-up. Can be conducted over phone.
- TTNS satisfaction survey at 3-month follow-up. Can be conducted over the phone.
- Information will be tabulated on an Excel spreadsheet on my personal work desktop, password protected. Any paper data (bladder diary) will be de-identified and retained in a locked drawer in the locked office of the PI.
- General self-efficacy at baseline, week 6 and at the end of the trial. Can be conducted over the phone.
- CD-RISC at baseline, week 6 and at the end of the trial. Can be conducted over the phone.
- The medication and TTNS adherence survey at baseline then every 4 weeks. Can be conducted over the phone.
- The medication and TTNS % survey at baseline then every 4 weeks. Can be conducted over the phone.

1. Summary of Study Design

A randomized control trial of TTNS v sham-control in chronic SCI (n=60) performing intermittent catheterization on OAB medications will be performed to address the following Specific Aims:

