Subjects will have their first study visit after their normal clinic visit. Once consented, we will trial TTNS for a response of toe flexion. If they have a response, they will be included in the study. If no response or not tolerating electric stimulation, they will not be included in the study.

Participants will have direction in clinic on the use of the Stamobil+, including written, oral, and smartphone images/video if they have access.

The electric stimulation protocol will use stimulation frequency of 10 Hz and pulse width of 200ms in continuous mode for 30 minutes daily, beginning as soon as possible. The goal is 5 days per week of TTNS use for 3-months.

Subjects will be called weekly to capture the information of the TTNS log and to monitor progress of protocol. They will also be reminded to change electrodes weekly. 3 days prior to the NBSS call, the RA will contact the subjects to remind them to begin recording in their voiding diary for 2 days.

- *Final Study Visit:*

Upon completion of the 3-month study period, final voiding diary information will be collected and the post-trial questionnaires will be conducted.

- *Post Study Follow up and Procedures*

The data will be statistically analysed in the post-study follow up. Subject participation is not required.

- *Discontinuation Visit and Procedures*

If withdrawal occurs, no evaluation will be required for the final study visit, regardless of the withdrawal reason. There are no safety risks in withdrawing from this study at any point. OAB medications can be resumed at the prior efficacious dose.

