The Data Safety Monitoring Plan (DSMP) for the research study includes periodic statistical analysis on rates of morbidity of study participants compared to controls by the PI and the statistician. Because of the rolling recruitment in the proposed protocol, we anticipate the number of recruited individuals will be sufficient for morbidity review quarterly.

Specifically, we will focus on the occurrence of UTI. We hypothesize that the rate of UTIs in TTNS group will be similar to the SCI population. Based on literature, the overall rate of UTI in SCI is about 2.5 episodes per patient per year. As a result, we expect to see 0.6 episodes per patient during the 3-month study period. Based on that, we construct the stopping rules to stop at 20% UTI rate using lower 90% exact Blyth-Still-Casella confidence bounds. If the number of patients with UTI exceed 3 in the first 5 patients, 4 in the first 10 patients, or 5 in the 14 patients, then patient accrual will be paused pending a review by a medical advisory board comprised of SCI experts.

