11. SAMPLE SIZE AND STATISTICAL METHODS

1. Determination of Sample Size

Sample size will be determined from **Aim 1.1**. Assuming that 40% of the subjects in the control group are able to reduce their bladder medications (placebo effect), the study would require a sample size of 21 for each group (i.e. a total sample size of 42), to achieve a power of 80% for detecting a difference in proportions of 43% between the two groups (83% in TTNS group –40% in control group) at a two sided p-value of 0.05. Accounting for 40% dropout, we will recruit 30 subjects in each arm for a total of 60 subjects. In **Aim 1.2**, the NBSS has demonstrated responsiveness to change after bladder chemodenervation with a mean difference of 11.8 (11),²² which would require a sample size of 20. For **Aim 2.1**, a 7±17 point improvement in the I-QOL score was observed after 4 weeks of TTNS use in our pilot study. We expect the control group to have minimal improvement in I-QOL scores due to placebo effect, estimated as 3 points. With power of 80% and a more conservative standard deviation of 4 points, we need a sample size of 22 in total by two-sample two-sided t-test at a type I error rate of 0.05. The sample size determined by Aim 1.1 is sufficient for this aim.

2. Statistical and Analytical Plans

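### The plan waives evaluation after any withdrawal and does not continue adverse event contact, so the by-arm morbidity comparison may rest on unequal, informatively censored observation of unknown size

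*Combined protocol and SAP*

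**What the plan says.** Section 6, Study Visits and Procedures, under the discontinuation visit: "If withdrawal occurs, no evaluation will be required for the final study visit, regardless of the withdrawal reason". It goes on: "There are no safety risks in withdrawing from this study at any point".

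The schedule of events in section 5 has adverse event reporting at baseline and every week to week 12, by phone. It does not say what happens to these calls once someone has withdrawn.

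Section 3, Withdrawal Criteria, introduces its list as "Possible reasons for discontinuation of study intervention". The first item is "Intolerable incontinence after discontinuation of bladder medications". The next heading says that dropouts will be replaced.

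Section 9, Safety Monitoring Plan, provides for "periodic statistical analysis on rates of morbidity of study participants compared to controls by the PI and the statistician", with a focus on UTI and a quarterly review. It does not define the denominator. The accrual pause rule in the same section counts patients with a UTI among the first 5, 10 and 14 patients, without reference to arm.

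Section 11, Determination of Sample Size, assumes that 83% of the TTNS group and 40% of controls reduce their medication, and then says: "Accounting for 40% dropout, we will recruit 30 subjects in each arm". Section 5 anticipates 6 dropouts among 60.

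**The concern.** Section 3 places stopping the intervention under withdrawal, and section 6 asks for nothing after withdrawal. A site that follows the text can therefore close the harm record on the day a participant stops, and the week-12 adverse event entry goes with the waived final contact.

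That matters most if stopping depends on arm. Medication is withdrawn in both arms, and the trial's hypothesis is that TTNS preserves continence during this better than sham does. Withdrawal for intolerable incontinence could then occur more often, and earlier, in sham. UTIs in those participants would go unrecorded unless found by another route. If the two arms had the same true UTI rate, a count of patients with a UTI would then make TTNS look worse. If participants who leave also differ in their underlying UTI risk, a rate per unit of time could be distorted too, in a direction that cannot be predicted.

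**Working it through.** **Reproducing the plan's figure.** 2.5 UTIs per patient-year × 3/12 = 0.625, which agrees with the stated 0.6 per patient over the study (sections 2 and 9).

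**Inputs from the documents.** 0.6 UTIs per patient over 12 weeks; 30 per arm; reduction in 40% of sham and 83% of TTNS, so 60% and 17% do not reduce (section 11); first medication change at week 3 and 6 anticipated dropouts (section 5).

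**Assumptions not in the documents.** The same constant UTI rate in both arms (0.6/12 = 0.05 per week); withdrawals only among non-reducers; a share f of non-reducers withdraws; withdrawal time t uniform over weeks 3–12 or weeks 3–7; nothing recorded after withdrawal; no replacement.

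**Formulas.**
- Share withdrawing: w = 0.60f (sham), 0.17f (TTNS).
- Share of expected events lost: w × mean(1 − t/12). The mean is 0.375 for weeks 3–12 and 0.583 for weeks 3–7.
- Completers with at least one UTI: 1 − exp(−0.6) = 45.1%.
- Withdrawals with a recorded UTI: 1 − mean of exp(−0.05t). Weeks 3–12: 1 − (e^−0.15 − e^−0.60)/(0.05 × 9) = 30.7%. Weeks 3–7: 1 − (e^−0.15 − e^−0.35)/(0.05 × 4) = 22.0%.
- Observed proportion in an arm: (1 − w) × 45.1% + w × (30.7% or 22.0%).

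For the 6 dropouts, f = 6/(18 + 5.1) = 0.26, where 18 = 30 × 0.60 and 5.1 = 30 × 0.17.

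| Scenario | Withdrawals, sham / TTNS | Timing (weeks) | Events lost, sham / TTNS | Patients with UTI, sham / TTNS | Difference |
|---|---|---|---|---|---|
| No non-reducer withdraws (f = 0) | 0 / 0 | – | 0 / 0 | 45.1% / 45.1% | 0 |
| 6 dropouts (f = 0.26) | 4.7 / 1.3 | 3–12 | 5.8% / 1.7% | 42.9% / 44.5% | 1.6 points |
| | | 3–7 | 9.1% / 2.6% | 41.5% / 44.1% | 2.6 points |
| Half withdraw (f = 0.5) | 9 / 2.6 | 3–12 | 11% / 3% | 40.8% / 43.9% | 3.1 points |
| | | 3–7 | 17.5% / 5% | 38.2% / 43.2% | 5.0 points |
| All withdraw (f = 1) | 18 / 5.1 | 3–12 | 22.5% / 6.4% | 36.5% / 42.7% | 6.2 points |
| | | 3–7 | 35% / 9.9% | 31.2% / 41.2% | 9.9 points |

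**Check on observation time.** With every withdrawal at week 6, mean weeks observed = 12(1 − w) + 6w. At f = 1 this is 8.4 in sham and 11.0 in TTNS, a ratio of 0.77. At f = 0.26 the ratio is 0.94, and at f = 0 it is 1.00.

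**Effect of a person-time denominator.** Take f = 1, weeks 3–12. Sham: 18 × (1 − 0.225) = 13.95 events over 30 × 12 × 0.775 = 279 person-weeks, or 0.05 per week. TTNS: 18 × (1 − 0.06375) = 16.85 events over 337 person-weeks, also 0.05. With constant, equal rates the bias vanishes. It remains only if those who leave have a different risk from those who stay.

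**The case against.** A reader might infer that failed weaning is a listed withdrawal reason, expected in 60% of sham and 17% of TTNS, so that sham is certain to be observed for less time. The documents do not support this. The listed reason is intolerable incontinence, and section 5 describes what follows a failed wean: "If the subject does not tolerate weaning, they will remain on the lowest, tolerable dose and we will attempt weaning the following week". Those participants stay in the trial. The 60% and 17% are failures on the endpoint among participants assessed, and section 11 adds dropout on top of them. That their average (38.5%) lies near the 40% dropout allowance is a coincidence between two different quantities.

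Other points also stand:
- Section 6 waives the evaluation at the final visit. It leaves the weekly calls after withdrawal unaddressed and does not cancel them.
- Section 5 gathers morbidity from interview, exam and EMR review, so some events could be found that way, although nothing says this continues after withdrawal.
- Section 9 speaks of rates for the comparison with controls. The patient count belongs to the pause rule, which is not by arm. It would therefore be wrong to say that the comparison is biased as planned.
- Replacement of dropouts adds observation time that the table ignores.
- With 30 per arm, the 95% confidence interval for a difference has a half-width of about 25 points (1.96 × √(2 × 0.451 × 0.549/30)), much wider than any distortion in the table. Under equal rates the distortion makes TTNS look worse.

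These points limit the size and certainty of the problem. They do not supply a rule that keeps harm follow-up going.

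**Conclusion.** The concern holds as a gap with a plausible imbalance between arms, not as a demonstrated bias. As written, the plan waives evaluation after withdrawal for any reason, does not separate stopping the intervention from leaving follow-up, and plans a comparison of morbidity with controls without a stated denominator. If TTNS works as assumed, one listed reason for stopping may fall more on sham.

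The size cannot be known from the documents. Under the assumptions above it is zero if no non-reducer withdraws, under 3 points in patients with a UTI with 6 dropouts, and about 6 to 10 points only if every non-reducer withdraws, an extreme case that sits badly with section 5. The point merits action because the remedy is cheap.

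**What to change.** **Section 6, Study Visits and Procedures.** Separate stopping the intervention from leaving follow-up, and replace the waiver with a sentence such as: *Every randomized participant, including one who stops the intervention for any reason, continues the scheduled weekly adverse event and UTI phone contact to week 12 unless consent to contact is withdrawn; where consent permits, EMR review is the backup.*

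**Section 9, Safety Monitoring Plan.** Report UTI by arm as events per person-week observed, with a rate ratio and 95% confidence interval, alongside the number of patients with a UTI. Continued contact is the main remedy, because a person-time denominator alone does not deal with informative censoring.

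**To reconcile.** Section 1, Rationale for Study Design, says "After 2 weeks of home stimulation, those that are on bladder medicine will discontinue the medication", whereas section 5 describes stepwise weaning with retries. The sponsor should make these agree, since they bear on how often the incontinence reason could arise. The 6 dropouts in section 5 (6/60 = 10%) should also be reconciled with the 40% in section 11 (0.40 × 60 = 24).

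**Cost.** One protocol sentence and one analysis sentence. The calls are already scheduled, so no new visit or staff is needed. The downside is a few more calls to people who have stopped, some of whom will decline.

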7. TRIAL MATERIALS

The electric stimulation device used for TTNS is the Stamobil +.

1. Trial Product (s)

The Stamobil + is a class II medical device that requires a prescription for use. It is a multifunction electrotherapy device currently used at TIRR Memorial Hermann for the purpose of motor and sensory recovery in people with paralysis. It has the ability to provide conventional neuromuscular electric stimulation (NMES), transcutaneous electric nerve stimulation (TENS) and Pulsed Galvanic Stimulation electrotherapy. The device has wide-ranging capability and programmability, with stimulation and wave parameters adjusted for the proposed study purpose. The FDA Approved indications are:

As an NMES device, indications are for the following conditions:

- Retarding or preventing disuse atrophy
- Maintaining or increasing range of motion
- Re-educating muscles
- Relaxation of muscle spasms
- Increasing local blood circulation
- Prevention of venous thrombosis of the calf muscles immediately after surgery

As a TENS device, indications are for the following conditions:

- Symptomatic relief and management of chronic, intractable pain
- Adjunctive treatment for post-surgical and post-trauma acute pain
- Relief of pain associated with arthritis

As a Pulsed Current device, indications are for the following conditions:

- Reduction of edema (under negative electrode)
- Reduction of muscle spasm
- Influencing local blood circulation (under negative electrode)
- Retardation or prevention of disuse atrophy
- Facilitation of voluntary motor function
- Maintenance of increase of range of motion

As a functional electrical stimulation (FES) device, the indications for the following condition:

- Stimulation of the leg and ankle muscles of partially paralyzed patients to provide flexion of the foot, thus improving the patient's gait

2. Storage and Drug Accountability

There are no special storage needs for the device. They will be stored in the locked office of the PI in a dry, dedicated place.

8. TREATMENT

1. Rationale for Selection of Dose

Neuromodulation of the bladder is currently available with percutaneous TNS in the clinic setting, for a variety of patient populations. Stimulation frequency of 10 Hz and pulse width of 200ms in continuous mode will be used.^{13,14}

Neuromodulation of the bladder has been shown to be effective after 6-8 sessions, with sessions performed once weekly over 12 weeks or 3 times weekly. The 30 minute stimulation session is commonly used for bladder neuromodulation.^{23, 24}

2. Study Drug Formulations

NA

3. Study Drug Administration

NA

4. Specific Restrictions / Requirements

NA

5. Blinding

NA

6. Concomitant therapy

Medications that may have an effect upon the bladder will be recorded. The medication classes include: 1) bladder medications, 2)anti-spasm medications, 3) anti-depressants/anxiolytics; 4) neuropathic pain medications.

9. SAFETY MEASUREMENTS

1. Definitions

An adverse event is any unfavourable and unintended sign, symptom, or disease temporally associated with the use of a medical treatment or procedure that may or may not be considered related to the medical treatment or procedure.

The FDA definition of unanticipated adverse device effect will be used, as followed: *An unanticipated adverse device effect* as defined by FDA regulations at 2CFR 812.3(s) – Any serious adverse effect on health or safety or any life-threatening problem or death caused by, or associated with, a device, if that effect, problem, or death was not previously identified in nature, severity, or degree of incidence in the investigational plan or application (including a supplementary plan or application), or any other unanticipated serious problem associated with a device that relates to the rights, safety, or welfare of subjects.

Skin irritation, inflammation, and electrode burn beneath the electrodes are potential adverse events directly related to the use of electric stimulation.

2. Collecting, Recording and Reporting of Adverse Events

The Investigator will be responsible for collecting and reporting adverse events during the UDS. The research assistant and the PI will collect adverse events related to the randomized control trial.

Grading of the severity of the adverse events will be made by the PI, using the Common Terminology Criteria for Adverse Events v4.0 developed by the National Cancer Institute. The relevant “Burn” category is included below.

DERMATOLOGY/SKIN						Page 1 of 3
Adverse Event	Short Name	Grade				
		1	2	3	4	5
Burn	Burn	Minimal symptoms; intervention not indicated	Medical intervention; minimal debridement indicated	Moderate to major debridement or reconstruction indicated	Life-threatening consequences	Death

REMARK: Burn refers to all burns including radiation, chemical, etc.

Reporting procedures for:

- Deaths and life-threatening events
- other SAEs
- Other adverse events

The PI will report problems according to the UTHSC-Houston IRB policy, specifically in the event which in the opinion of the PI is both unexpected and related and places subjects or others at risk of harm.

The PI will report the reportable events to CPHS via iRIS within 7 days, unless the report involves the death of a participant, in which case the report needs to be provided to CPHS within 24 hours.

3. Safety Monitoring Plan

The Data Safety Monitoring Plan (DSMP) for the research study includes periodic statistical analysis on rates of morbidity of study participants compared to controls by the PI and the statistician. Because of the rolling recruitment in the proposed protocol, we anticipate the number of recruited individuals will be sufficient for morbidity review quarterly.

Specifically, we will focus on the occurrence of UTI. We hypothesize that the rate of UTIs in TTNS group will be similar to the SCI population. Based on literature, the overall rate of UTI in SCI is about 2.5 episodes per patient per year. As a result, we expect to see 0.6 episodes per patient during the 3-month study period. Based on that, we construct the stopping rules to stop at 20% UTI rate using lower 90% exact Blyth-Still-Casella confidence bounds. If the number of patients with UTI exceed 3 in the first 5 patients, 4 in the first 10 patients, or 5 in the 14 patients, then patient accrual will be paused pending a review by a medical advisory board comprised of SCI experts.

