4. TRIAL SCHEDULE

Table 3. Study Timeline

Task	Year 1				Year 2			
	1	2	3	4	1	2	3	4
Obtain IRB approval								
Register study with www.clinicaltrials.gov								
Subject screening and recruitment (n=60, ~2-6/month)								
Baseline assessments								
Neurogenic Bladder Symptom Score (NBSS) (SA 1.2)								
Incontinence quality of life (I-QOL) (SA 2.1)								
Anticholinergic Side Effects (SA 2.2)								
Collection of Voiding Diary Weekly								
Overactive Bladder Medication dosage (SA 1.1)								
Cath frequency, volumes, and incontinence (SA 1.2)								
Compliance								
Evaluate the efficacy of TTNS at home (SA 1)								
Evaluate the impact of TTNS on quality of life (SA 2)								
Analyze SA 1 & SA 2								
Present findings								
Development of manuscript(s)								

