5. STUDY DESIGN

Anticipated number of patients to screen: 80

- Anticipated number of patients to enroll: 60
- Anticipated drop out or loss to follow-up: 6

Approximate time to complete study recruitment: 1 year

Expected duration of subject participation: 3-months. 3-months was selected as a fair assessment of efficacy. Clinically, medications are determined efficacious based on 1-month or less of use.

TTNS protocol: Same TTNS setting will be used as protocols HSC-MS-15-0806 and HSC-MS-17-0423. Electrodes 2 inch by 2 inch will be placed according to anatomic landmarks, with the negative electrode behind the internal malleolus and the positive electrode 10cm superior to the negative electrode, verified with rhythmic flexion of the toes secondary to stimulation of the flexor digitorum and hallucus brevis. The intensity level will be set to the amperage immediately under the threshold for motor contraction. If there is not contraction seen, patients will be excluded. In addition, if the patient perceives pain, the intensity will be lowered until comfortable. Stimulation frequency of 10 Hz and pulse width of 200ms in continuous mode will be used.^{13, 14}

Sham protocol and rationale: Toe flexion will be attempted, as in the TTNS protocol. Then the stimulation will be reduced to 1 mA for 30 minutes. Rationale: In order to make this a convincing blind, the TTNS protocol must be simulated closely as subjects may interact and discuss. Rather than turning the device off, they will be instructed that the stimulation required is below motor threshold, at 1 mA. Based on the knowledge of the pilot trial requiring about 40mA for TTNS, and the amperage for needle-driven PTNS adjacent to the tibial nerve at 0.5 – 1mA, it is unrealistic that 1mA via surface electrodes is sufficient to activate the tibial nerve. Both TTNS and sham participants will be instructed to use the device for 30 minutes, 5 days per week.

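### The UTI accrual-pause rule sets a 20% share-of-patients reference that is not derived from the 0.6 episodes per patient it cites, and its 5-patient trigger does not follow from the stated 90% bound.

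*Combined protocol and SAP*

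**What the plan says.** The same rule appears in section 2.4.c (End Points - Safety) and section 9.3 (Safety Monitoring Plan) of the combined protocol and SAP. Both start from a literature rate of 2.5 UTI episodes per patient per year and conclude that "we expect to see 0.6 episodes per patient during the 3-month study period". Presenting the next step as based on that figure, they continue: "we construct the stopping rules to stop at 20% UTI rate using lower 90% exact Blyth-Still-Casella confidence bounds".

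The count that triggers action is of patients with a UTI. Action follows if that number should "exceed 3 in the first 5 patients, 4 in the first 10 patients, or 5 in the 14 patients", and the action is: "then patient accrual will be paused pending a review by a medical advisory board comprised of SCI experts". Taken literally, the triggers are at least 4 of 5, 5 of 10 and 6 of 14.

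Section 9.3 also gives the no-harm expectation: "We hypothesize that the rate of UTIs in TTNS group will be similar to the SCI population". It provides for a quarterly review of morbidity against controls. Neither section says which arm(s) supply the patients counted, or how long each must have been followed.

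**The concern.** Episodes per patient and the share of patients with at least one episode are different scales. The rule moves from the first to the second without a conversion. If the 20% reference lies below the share that the plan's own background rate implies, ordinary background UTIs can pause accrual more often than a 20% basis suggests. The protocol does not say that 20% was deliberately set below background.

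The printed triggers should also be reproducible from the named interval and level, and one is not. This is the only numerical safety boundary in the plan, and it acts on the first 14 of 60 planned patients. Efficacy endpoints and analyses are not affected.

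**Working it through.** **Inputs from sections 2.4.c and 9.3.** Rate 2.5 per year, so 2.5/4 = 0.625 per 3 months, printed as 0.6. Reference 20%. Triggers at least 4/5, 5/10 and 6/14. The distribution of UTIs between patients is not given, so the Poisson and negative binomial forms below are assumptions.

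**1. The plan's triggers against its stated method.** A Blyth-Still-Casella lower limit exceeds 20% when the observed count lies above the shortest acceptance set at p = 0.20.

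| n | 90% set (probability) | first count above | 95% set (probability) | first count above | printed |
|---|---|---|---|---|---|
| 5 | 0-2 (0.942) | 3 | 0-3 (0.993) | 4 | 4 |
| 10 | 0-4 (0.967) | 5 | 0-4 (0.967) | 5 | 5 |
| 14 | 1-5 (0.912) | 6 | 0-5 (0.956) | 6 | 6 |

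At 90% the 10- and 14-patient triggers are reproduced. The 5-patient trigger is not, because the lower limit at 3/5 is already 0.247. The 95% two-sided version gives all three.

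A two-sided 90% (one-sided 95%) Clopper-Pearson limit also gives all three: 3/5 0.189, 4/5 0.343; 4/10 0.150, 5/10 0.222; 5/14 0.153, 6/14 0.206. A one-sided 90% Clopper-Pearson limit does not (3/5 0.247).

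**2. Share of patients with at least one UTI in 3 months.**
- Poisson, 1 - exp(-m): 1 - exp(-0.6) = 0.451; 1 - exp(-0.625) = 0.465.
- Negative binomial, 1 - (k/(k + 0.6))^k: 0.433 (k = 5), 0.375 (k = 1), 0.326 (k = 0.5), 0.264 (k = 0.25), 0.177 (k = 0.1).
- For any distribution with mean 0.6, a 20% share requires 0.6/0.20 = 3 episodes per affected patient. In the negative binomial this is k of about 0.13.
- One-month count, Poisson: 1 - exp(-0.6/3) = 0.181; 1 - exp(-0.625/3) = 0.188.

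**3. Chance that the printed rule is crossed by patient 14.** Exact binomial recursion over the three looks, independent patients, no excess risk. Paired figures are for means 0.6 and 0.625.

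| Scenario | Share with UTI | P(pause) |
|---|---|---|
| True 20% | 0.200 | 0.056 |
| 3 months, Poisson | 0.451 / 0.465 | 0.689 / 0.724 |
| 3 months, k = 1 | 0.375 / 0.385 | 0.467 / 0.496 |
| 3 months, k = 0.25 | 0.264 / 0.269 | 0.160 / 0.172 |
| 3 months, k = 0.1 | 0.177 / 0.180 | 0.034 / 0.036 |
| 1 month, Poisson | 0.181 / 0.188 | 0.038 / 0.044 |

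A full 3-month count is workable. Section 5 gives "Anticipated number of patients to enroll: 60" and "Approximate time to complete study recruitment: 1 year", so average accrual is 60/12 = 5 per month. Patient 14 enrols at about 13/5 = 2.6 months and completes 3 months at 5.6 months, well before accrual ends.

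**4. Counting instead at the moment patients 5, 10 and 14 enrol.** Simulation with evenly spaced accrual and a constant hazard for each patient.
- Both arms, 5 per month: 6-7% (Poisson) or 1.0-1.2% (k = 0.25), against 0.07-0.2% at a true 20%.
- TTNS arm only, 2.5 per month: 29-32% (Poisson) or about 5% (k = 0.25), against 0.8-1.2% at a true 20%.
- Both arms over the 2 to 6 per month in Table 3: about 40% down to 3% (Poisson) and 6.5% down to 0.6% (k = 0.25).

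**The case against.** **20% may be a monthly figure.** 0.6/3 = 0.2 episodes per patient-month, and the one-month Poisson share is 18-19%. On that reading the background pause chance is 3.8-4.4%, below the 5.6% at a true 20%, and the concern about excess pauses disappears. This is a plausible origin. However, the text ties its expectation to the 3-month period and states no one-month window, so it remains conjecture.

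**Clustering could be stronger than k = 0.25.** At k = 0.1 the share is 18% and the pause chance 3.4-3.6%. The documents cannot settle this. It follows that one cannot say the rule over-triggers in every case.

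**The method name may be right.** This stands in part. A 95% two-sided Blyth-Still-Casella interval gives all three triggers, so the level may be what is misstated. A non-literal reading may also be possible: take exceed as reach and 90% as one-sided (80% two-sided). Then 3/5 and 5/14 match, but 4/10 depends on how a tie between equally short acceptance sets is broken, and the standard refinement gives 0.188, below 20%.

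**A trigger below background is a legitimate cautious choice.** Crossing it only brings in SCI experts, and the quarterly comparison with controls helps separate background from excess UTIs. All of this is true and softens the consequence. It does not supply the missing derivation, and the text presents 20% as based on the 0.6 figure rather than as a deliberate margin.

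**Conclusion.** The point holds in two parts.

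First, on the 3-month period that the plan states, a 20% share of patients does not follow from 0.6 episodes per patient. The implied share is about 45% (Poisson) or 26-43% (k = 5 down to 0.25, assumed). With a full 3-month count and no excess risk, the chance of a pause by patient 14 is then 69-72% (Poisson) or 16-17% (k = 0.25), against 5.6% at a true 20%.

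Second, on the literal wording, the three triggers do not all follow from a 90% Blyth-Still-Casella bound. The effect is one patient at one look, and it makes the printed rule slightly less sensitive.

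A reader might go further and infer that the trial will probably pause on background UTIs, that the rule over-triggers whatever is assumed, or that the interval method is misnamed. The documents support none of these. The pause probability depends on the arm(s), the window and the clustering, all unstated. A one-month count or clustering near k = 0.1 reverses the direction. Either the method or the level could be the slip.

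The issue should be fixed, but it is limited to an accrual pause for advisory review. Confidence is medium, because the size rests on assumptions that the plan leaves open.

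**What to change.** Make matching edits in sections 2.4.c and 9.3:

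1. Reconcile the 20% reference with the 0.6-episode expectation on one scale: the share of patients with at least one UTI over a stated follow-up window and in stated arm(s), with the distributional assumption given. Alternatively, state that 20% is deliberately below background, and why.
2. Recompute or confirm the three boundaries, and state the method and confidence level (one- or two-sided) that produce them.
3. Report the probability of a pause at the expected background rate.

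The choice of threshold stays with the sponsor and its advisory board; no replacement boundary is proposed here.

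The cost is a short recalculation and a few sentences. If 20% was deliberate, an explanation, the method check, the counting definition and the background pause probability are enough. The downside is that a recalculated rule may trigger review more or less readily; item 3 makes the pause chance at background visible.
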